**6.6.2.f** In patients who consent to optional biopsies, an early response tumor sample will be obtained 1-12 weeks after starting the selected therapy. This biopsy should take place after completion of the repeat PET imaging and should target the same tumor site as the baseline biopsy. A whole blood sample may be drawn for correlation of steroid hormone levels in serum and biopsy tissue.

**6.6.2.g Week 1 to 20 years after [F]FES PET Scan:** Clinical follow-up will continue for up to 20 years, time of progression and date of death will be

recorded. For some patients, especially those receiving two endocrine-directed treatments, a third FES PET scan and additional research FDG PET scan may also be obtained 1-12 weeks after the second FES PET scan. For each patient, a maximum of 3 FES PET and 3 FDG PET scans would be done.

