#### **6.10.2.c Quantitative Assessment**

FES static survey images will undergo region of interest (ROI) analysis as follows: Lesion location will be identified using FES scans along with FDG scans with reference to CT or ultrasound. All patients will have undergone clinically motivated FDG PET scans for staging prior to FES imaging. CT, MRI, ultrasound or bone scan will be available on all patients with suspected metastatic disease. Although FES and FDG imaging will be performed on separate days, studies will be performed with the patient in the same position and images will be co-registered using common anatomic landmarks such as the lung outline, cardiac blood pool, liver contour, and body outline. In this way, regions can be drawn on the FDG images and transferred to the FES images for quantitative analysis which is important in identifying tumor locations, especially in ER-negative tumors which are not visualized on FES imaging. For each disease site, a set of 1.5 cm diameter regions on three adjacent planes with the highest lesion FES uptake will be drawn to determine maximal FES uptake. Up to the 10 largest sites seen on the static torso survey will be quantified. Partial-volume correction will not be used because only sites 1.5 cm or greater diameter will be included in quantitative analysis.

FES uptake will be quantified using the standard uptake value (SUV, defined below). For each site, we will record the average and maximum SUV within the ROI set for each site of disease.

For each subject, we will calculate the average and range of FES uptake values for active disease sites. The FES uptake will be compared with subsequent response to endocrine therapy and TTP.

FDG studies will also be quantified for uptake in a similar fashion. On FDG studies, simple SUVs will be generated using the average tissue activity over the imaging period, which are typically 45 and 75 minutes after injection. We will record the maximum FDG SUV for each site of

disease. Uptake at tumor sites using the standardized uptake value (SUV) is calculated as:

$$SUV = \frac{\overline{C}_t}{ID / wt}$$

where  $\overline{C}_t$  is the average tumor uptake after injection for the period of the static imaging for torso surveys (MBq/mL), ID is the injected dose (GBq) and wt is the patient's weight (kg). Note that either standard or metric units can be used to calculate SUV as long as only one type of unit is used for each calculation.

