## **6.12 MEASUREMENT OF EFFECT**

For the purposes of this study, the outcome measured will be the change in FES and FDG PET measures between the serial sets of scans. Response evaluations will not be evaluated as part of this study, though the information may be recorded if it is collected for treatment studies the patient may be participating. Patients may also be followed for up to 20 years for disease progression and overall survival.

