### **6.12.1 Time to Progression**

Time to progression (and progression-free survival) will be measured as the time from the start of endocrine therapy to the time the patient is first recorded as having disease progression. If a patient never progresses while being followed, the patient will be censored at the time he/she terminates follow-up or by date of disease progression or death.

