## **6.14 STATISTICAL CONSIDERATIONS**

### **6.14.1 Analysis Plan**

The primary application will be pilot studies with enrollment of about 20 patients, in which the in vivo effects of endocrine-targeted therapy are measured by serial FES PET. The primary endpoints will be quantitative and qualitative measures of FES uptake, and measures of change in FES uptake (Section 6.10.2). Additionally, patients will be followed for disease progression. Associations among FES and FDG PET measures, progression, and biological correlates (Section 6.10.3) may be examined in descriptive analyses.

An expected primary analysis is to examine whether FES uptake changed on average between serial assessments. This may be assessed by a one-sample test of the percent change in FES SUV. For example, a one-sided test at the 0.05 level of significance could evaluate whether the average

percent change in FES SUV was greater than 20%, considered a biologically significant change. In serial FES SUV measurements of heavily-pretreated breast cancer patients, change in FES SUV was approximately normally distributed with a standard deviation of about 25 percentage points, for both patients treated with blocking therapy (tamoxifen or fulvestrant) or non-blocking therapy (aromatase inhibitor). Using this standard deviation and n=20 to test whether the average change was greater than 20%, the power would be 0.97 if the true change is 40%, and 0.85 if the true change is 35%. To conclude only that the average percentage change was different from zero (using a two-sided test at the 0.05 level of significance), power would be 0.95 to detect a true average change of 20% (and 0.85 if the true standard deviation were 30 percentage points).

Other analyses for pilot studies could examine what proportion of patients experienced a threshold in percentage change, or surpassed a targeted follow-up FES SUV value. These percentages will be reported using a 90% Wilson score binomial confidence interval (Agresti, 1998). Width of these confidence intervals for pilot studies of n=20, n=25, and n=30 are given in Table 6.3 for a range of observed percentages.

**Table 6.3:** 90% Wilson score binomial confidence intervals (CIs) by percent observed and sample size.

observed percentage (CI) for n=20	observed percentage (CI) for n=25	observed percentage (CI) for n=30
0.1 (0.03, 0.26)	0.12 (0.05, 0.27)	0.1 (0.04, 0.23)
0.2 (0.09, 0.38)	0.20 (0.10, 0.36)	0.2 (0.11, 0.34)

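### Section 6.12.1 gives TTP and PFS one rule that censors deaths, so any PFS reported under it would be TTP under another name

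*Combined protocol and SAP*

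**What the plan says.** Section 6.12.1 opens with both endpoints under one definition: "Time to progression (and progression-free survival) will be measured as the time from the start of endocrine therapy" up to "the time the patient is first recorded as having disease progression". The next sentence deals with everyone else: "If a patient never progresses while being followed, the patient will be censored", and the dates allowed for this are given as "censored at the time he/she terminates follow-up or by date of disease progression or death".

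The related sections are these:

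- Section 6.12: "Patients may also be followed for up to 20 years for disease progression and overall survival".
- Section 6.6.2.g: "Clinical follow-up will continue for up to 20 years, time of progression and date of death will be" recorded.
- Section 6.10.2.c: "The FES uptake will be compared with subsequent response to endocrine therapy and TTP".
- Section 6.14.1: "Associations among FES and FDG PET measures, progression, and biological correlates (Section 6.10.3) may be examined in descriptive analyses".

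PFS is named only in 6.12.1. No section gives it a separate definition or makes death an event.

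**The concern.** TTP and PFS differ in one respect: how a death without prior progression is handled. TTP conventionally censors it, and PFS counts it as an event. A single rule cannot serve both, and the rule written here is the TTP one.

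A PFS reported from these data would therefore be TTP with a different label. It would be at least as favourable as true PFS, and a reader could not tell this from the label. Comparison with a conventionally defined PFS from another study would not be valid.

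Deaths without recorded progression are plausible. Section 6.4.1 admits patients with recurrent or metastatic disease, and follow-up may run to 20 years. Section 6.12 says that response is not evaluated as part of this study, so progression dates depend on what others record.

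Separately, the censoring sentence contradicts itself. A patient who never progresses has no progression date at which to be censored. This is a wording error that should have little effect on results, but it affects TTP as well, and TTP is the endpoint that 6.10.2.c compares with FES uptake.

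**Working it through.** The documents give no median, event count, hazard ratio or power for TTP or PFS, so there is no stated figure to reproduce. The check is one of definition, followed by an illustration of size.

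**1. Definition, patient by patient, under 6.12.1**

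| Patient | Rule in 6.12.1 (TTP and PFS) | Conventional PFS |
|---|---|---|
| Progression recorded | Event | Event |
| Dies, no progression recorded | Censored at death | Event at death |
| Alive, no progression recorded | Censored at end of follow-up | Censored |

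The second row is the whole difference.

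**2. Four-patient example.** Suppose one progression at month 6, deaths without progression at months 4 and 10, and one patient event-free at month 12.

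- Rule in 6.12.1: one event, with 3 at risk at month 6. The 12-month Kaplan-Meier estimate is 2/3 = 0.667.
- Deaths counted: three events. The 12-month estimate is 3/4 × 2/3 × 1/2 = 0.25.

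**3. General size.** Let s be the share of first events that are deaths without recorded progression. The documents do not give s; 0 to 20% is assumed. If the ratio of death hazard to progression hazard is constant over time, the PFS hazard equals the progression hazard divided by (1 − s). The curve under 6.12.1 is then S_reported(t) = S_PFS(t)^(1−s). At the true PFS median it reads 0.5^(1−s) instead of 0.5. This step does not need constant hazards. If the hazards are also constant, the median is multiplied by 1/(1−s).

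| Assumed s | Reported PFS at the true median | Factor on the median (constant hazards) |
|---|---|---|
| 0% | 0.500 | 1.00 |
| 5% | 0.5^0.95 = 0.518 | 1/0.95 = 1.05 |
| 10% | 0.5^0.90 = 0.536 | 1/0.90 = 1.11 |
| 20% | 0.5^0.80 = 0.574 | 1/0.80 = 1.25 |

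For example, if median TTP were 12 months (assumed), true median PFS would be 11.4, 10.8 and 9.6 months at s = 5%, 10% and 20%. The rule in 6.12.1 would report 12 each time.

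**4. Sensitivity to hazard shape.** With Weibull hazards of shape k, the factor is (1/(1−s))^(1/k). At s = 10% it is 1.14 for k = 0.8 and 1.07 for k = 1.5.

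**5. Comparison with sampling error.** Section 6.14.1 foresees pilots of about 20 patients. With 20 events, a 95% interval for an exponential median is the estimate times exp(±1.96/√20), that is 0.65 to 1.55 times the estimate. All the factors above lie inside that interval.

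**6. Direction.** In 20,000 simulated pilots of 20 patients with no other censoring, the Kaplan-Meier median with deaths censored was longer than the median with deaths counted in 40%, 65% and 89% of runs at s = 5%, 10% and 20%. It was never shorter.

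**The case against.** The strongest objection is that nothing in the plan uses PFS. It is a parenthesis in a section headed as TTP. It is absent from the objectives in 6.2 and from the primary endpoints in 6.14.1. The one comparison named, in 6.10.2.c, is with TTP, for which censoring deaths is accepted. Progression analyses are optional and descriptive. All of this stands, and it limits the consequence to any PFS that is actually reported. It does not make the definition correct: 6.12.1 states how PFS will be measured, and follow-up collects the data from which it could be reported.

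A second objection is that the censoring sentence is garbled, so its mention of progression or death may be a misplaced list of PFS events. This does not succeed. The governing verb is censored, and the sentence before it makes recorded progression the only endpoint. At most it shows that the intent for PFS is unclear, which is also a reason to reword.

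A third objection is that one such death need not change the median. That is right. With 20 patients, at least one such death occurs with probability 1 − (1−s)^20, which is 0.64, 0.88 and 0.99 at s = 5%, 10% and 20%. Set against the 40%, 65% and 89% above, the median is unchanged in about 38%, 26% and 10% of the runs that contain such a death. The curve itself is too high from each such death onward, until both curves reach zero.

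Finally, s is assumed throughout. The documents give no basis for a value, and if no patient dies before recorded progression the two measures coincide.

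**Conclusion.** The concern holds. Under 6.12.1 PFS and TTP are the same variable. The rule is acceptable for TTP and wrong for PFS. The error has one direction: reported PFS is equal to or better than true PFS.

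Its size rests on an assumed s of 0 to 20%. Over that range the reported proportion at the true median is 50.0% to 57.4% (constant hazard ratio), and the median is inflated by a factor of 1.00 to 1.25 (constant hazards). In a single 20-patient pilot this is within sampling error.

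The primary analysis of FES change, its stated power and the TTP comparison do not depend on the PFS definition. The point should be fixed because the definition is wrong as written and the correction is nearly free, but it does not threaten the study's main results.

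**What to change.** Make two edits to 6.12.1.

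1. Either delete the reference to PFS, or add a sentence such as: *PFS is the time from starting endocrine treatment to recorded progression or death from any cause, whichever comes first; patients with neither are censored when follow-up ends.* Leave TTP with deaths censored.
2. Remove disease progression from the list of censoring dates, so that a patient without recorded progression is censored for TTP at the earlier of end of follow-up and death.

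The cost is one or two sentences. Time of progression and date of death are already recorded under 6.6.2.g. No additional visits, patients or data items are needed, and the sample size is unchanged.

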## **6.13 DATA REPORTING/ REGULATORY CONSIDERATIONS**

Adverse event lists, guidelines, and instructions for AE reporting are described in Section 6.8.

### **6.13.1 Data Reporting**

The Principal Investigator is responsible for maintaining complete and timely, HIPAA-compliant electronic records of clinical and image datasets.

## **6.14 STATISTICAL CONSIDERATIONS**

### **6.14.1 Analysis Plan**

The primary application will be pilot studies with enrollment of about 20 patients, in which the in vivo effects of endocrine-targeted therapy are measured by serial FES PET. The primary endpoints will be quantitative and qualitative measures of FES uptake, and measures of change in FES uptake (Section 6.10.2). Additionally, patients will be followed for disease progression. Associations among FES and FDG PET measures, progression, and biological correlates (Section 6.10.3) may be examined in descriptive analyses.

An expected primary analysis is to examine whether FES uptake changed on average between serial assessments. This may be assessed by a one-sample test of the percent change in FES SUV. For example, a one-sided test at the 0.05 level of significance could evaluate whether the average

percent change in FES SUV was greater than 20%, considered a biologically significant change. In serial FES SUV measurements of heavily-pretreated breast cancer patients, change in FES SUV was approximately normally distributed with a standard deviation of about 25 percentage points, for both patients treated with blocking therapy (tamoxifen or fulvestrant) or non-blocking therapy (aromatase inhibitor). Using this standard deviation and n=20 to test whether the average change was greater than 20%, the power would be 0.97 if the true change is 40%, and 0.85 if the true change is 35%. To conclude only that the average percentage change was different from zero (using a two-sided test at the 0.05 level of significance), power would be 0.95 to detect a true average change of 20% (and 0.85 if the true standard deviation were 30 percentage points).

Other analyses for pilot studies could examine what proportion of patients experienced a threshold in percentage change, or surpassed a targeted follow-up FES SUV value. These percentages will be reported using a 90% Wilson score binomial confidence interval (Agresti, 1998). Width of these confidence intervals for pilot studies of n=20, n=25, and n=30 are given in Table 6.3 for a range of observed percentages.

**Table 6.3:** 90% Wilson score binomial confidence intervals (CIs) by percent observed and sample size.

observed percentage (CI) for n=20	observed percentage (CI) for n=25	observed percentage (CI) for n=30
0.1 (0.03, 0.26)	0.12 (0.05, 0.27)	0.1 (0.04, 0.23)
0.2 (0.09, 0.38)	0.20 (0.10, 0.36)	0.2 (0.11, 0.34)
0.3 (0.16, 0.48)	0.32 (0.19, 0.48)	0.3 (0.18, 0.45)
0.4 (0.24, 0.58)	0.40 (0.26, 0.56)	0.4 (0.27, 0.55)
0.5 (0.33, 0.67)	0.48 (0.33, 0.64)	0.5 (0.36, 0.64)

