## **6.10.2 [F]FES-PET Image Assessment**

### **6.10.2.a Summary of Assessment**

The FES PET scan will be assessed in multiple ways.

Qualitative FES uptake: all known disease sites positive vs. heterogeneous or absent FES uptake.

Quantitative FES uptake: SUVs in all lesions measured at baseline and repeat scan (and at third scan if indicated)

Quantitative change in FES uptake: percentage and SUV unit change in SUV between baseline and repeat FES PET scan

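### The four powers stated for n=20 treat the SD as known; a one-sample t-test gives 0.96, 0.83, 0.92 and 0.81 instead of 0.97, 0.85, 0.95 and 0.85

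*Combined protocol and SAP*

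**What the plan says.** Section 6.14.1 (Analysis Plan) describes the setting as follows: "The primary application will be pilot studies with enrollment of about 20 patients". The expected primary analysis asks whether FES uptake changed on average between scans: "This may be assessed by a one-sample test of the percent change in FES SUV". The text does not say whether this is a z-test or a t-test.

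Two versions of the test are given.

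- **Against 20%:** one-sided at 0.05. The criterion is "percent change in FES SUV was greater than 20%, considered a biologically significant change". At n=20, "the power would be 0.97 if the true change is 40%, and 0.85 if the true change is 35" percent.
- **Against zero:** two-sided at 0.05. Here "power would be 0.95 to detect a true average change of 20% (and 0.85 if the true standard deviation were 30 percentage points".

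The SD rests on earlier heavily pretreated patients, in whom "change in FES SUV was approximately normally distributed with a standard deviation of about 25 percentage points". Section 6.10.2.a (Summary of Assessment) defines the change measure as "percentage and SUV unit change in SUV between baseline and repeat FES PET scan".

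**The concern.** The SD is an approximate value from earlier patients, and the plan itself considers 30 as an alternative. The analysis would therefore estimate the SD from the patients in hand. With about 20 of them that means a t-test, whose power is lower than the known-SD formula suggests. These are the only power figures in the plan, and the case most affected is its one check on a larger SD.

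A smaller, related gap is that the text speaks of enrolling about 20 patients and then computes power at n=20. The endpoint needs two scans, so a patient without a usable repeat FES scan contributes no value to this test. The text does not say which count n=20 refers to.

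**Working it through.** **Inputs, all from section 6.14.1.** n = 20 and alpha = 0.05. Let d be the true mean change minus the null value.

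| Case | Test | d | SD | Stated power |
|---|---|---|---|---|
| A | one-sided against 20%, true change 40% | 20 | 25 | 0.97 |
| B | one-sided against 20%, true change 35% | 15 | 25 | 0.85 |
| C | two-sided against 0, true change 20% | 20 | 25 | 0.95 |
| D | two-sided against 0, true change 20% | 20 | 30 | 0.85 |

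**Standardised distance**, d × √20 / SD, with √20 = 4.472:

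- A: 4.472 × 20/25 = 3.578
- B: 4.472 × 15/25 = 2.683
- C: 4.472 × 20/25 = 3.578
- D: 4.472 × 20/30 = 2.981

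**Step 1: reproduce the plan's figures (SD known).** Power = Φ(distance − z), with z = 1.645 one-sided and 1.960 two-sided. The opposite tail is negligible.

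- A: Φ(1.933) = 0.973
- B: Φ(1.038) = 0.850
- C: Φ(1.618) = 0.947
- D: Φ(1.021) = 0.846

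Rounded to two decimals these are 0.97, 0.85, 0.95 and 0.85, so all four stated values are recovered.

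**Step 2: SD estimated from the sample.** Power = P(T > t), where T is noncentral t with 19 df and the noncentrality is the distance above. The critical values are t = 1.729 one-sided and 2.093 two-sided. Both tails are counted in the two-sided cases.

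| Case | Stated | t-test | Stated minus t-test (points) |
|---|---|---|---|
| A | 0.97 | 0.964 | 0.6 |
| B | 0.85 | 0.827 | 2.3 |
| C | 0.95 | 0.924 | 2.6 |
| D | 0.85 | 0.807 | 4.3 |

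A simulation of the t-test with 400,000 draws gave 0.965, 0.827, 0.924 and 0.808.

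**Step 3: can the stated powers be kept?** They could be approached by using z critical values with the estimated SD, but then the 0.05 level is lost. With 19 df, P(T > 1.645) is about 0.058 one-sided and P(|T| > 1.960) is about 0.065 two-sided. Holding 0.05 requires the t critical values and hence the powers in step 2.

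**Step 4: sample size at which the t-test recovers the stated values.**

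| n | A | B | C | D |
|---|---|---|---|---|
| 21 | 0.971 | 0.844 | 0.936 | 0.828 |
| 22 | 0.976 | 0.859 | 0.947 | 0.846 |

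n = 22 is the smallest at which all four round to at least the stated figures.

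**Step 5: if 20 is the number enrolled.** The documents give no loss rate, so one or two lost pairs are assumed for illustration only.

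| Evaluable pairs | A | B | C | D |
|---|---|---|---|---|
| 19 | 0.956 | 0.808 | 0.909 | 0.785 |
| 18 | 0.946 | 0.787 | 0.892 | 0.760 |

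One lost pair takes case D below 0.80; two take case B below it as well.

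**The case against.** The plan never names a t-test. On its own inputs, with the SD taken as given, the four figures are computed correctly, so the fault lies in an undeclared approximation rather than a slip in calculation. That stands as a description. It does not rescue the figures, because a plan that considers a true SD of 30 is not treating the SD as known, and step 3 shows that the stated powers and the stated 0.05 level do not go together once the SD is estimated.

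The inputs are also rough. Both the SD and the enrolment are approximate, and the tests are offered as examples. One point of SD matters about as much as the choice of test: at SD 24 the t-test gives 0.974, 0.853 and 0.942 for cases A to C, and at SD 26 the known-SD formula gives 0.964, 0.825 and 0.931. The plan states no power target that the lower values would miss. All of this stands, and it is why the point is minor.

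The question of evaluable pairs is separate from z versus t. Repeat FES PET is planned for all patients, and willingness to undergo serial imaging is an inclusion criterion (6.4.1.f). The permitted omission for patients on SERD therapies concerns repeat FDG PET, not FES PET (6.6.2.e). Nothing in the documents shows that losses would be material. That is fair: defining n is a useful clarification, and the main point does not depend on it.

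**Conclusion.** The point holds and is minor. The four stated powers are known-SD values. For a one-sample t-test at n=20 they should read 0.96, 0.83, 0.92 and 0.81, which are 0.6 to 4.3 percentage points lower. The largest gap is in the SD-30 case, where the apparent margin of five points above 0.80 shrinks to less than one.

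No decision changes. With 20 evaluable patients every power stays above 0.80, and enrolment need not change. The conclusion assumes that the SD is estimated from the analysed patients, that percent change is approximately normal with the plan's SDs, and that 20 patients supply both scans.

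**What to change.** In section 6.14.1:

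1. Name the test as a one-sample t-test of percent change in FES SUV.
2. Restate the four powers as 0.96 and 0.83 (one-sided against 20%, SD 25) and 0.92 and 0.81 (two-sided against zero, SD 25 and SD 30).
3. Add a clause saying that n=20 means patients with evaluable baseline and repeat FES scans.

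A note that the figures are a normal approximation with the SD taken as known would be accurate about their origin, but it would leave the plan without the power of the test actually used. Restating them is better and no harder.

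The cost is four numbers, the name of the test and one clause. Enrolment, visits and the analysis are unchanged.

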This protocol is outlined in the following schematic. Briefly, patients with primary, recurrent or metastatic breast cancer from an ER+ primary tumor who will be undergoing endocrine-targeted therapy will be imaged with [F-18]-16 $\alpha$ -fluoroestradiol. All patients will undergo a pre-therapy FES PET or FES PET/CT scan (hereafter FES PET will be used to denote both FES PET and FES PET/CT unless specifically noted). In some patients receiving non-interfering medications such as aromatase inhibitors, scans may be performed with patients already on a treatment who are to start an alternative or additional endocrine targeted treatment. Patients will undergo a repeat FES PET and FDG PET on study after starting the endocrine-targeted therapy. The exact timing of the repeat scans may vary depending on the treatment regimen. In the repeat studies, we will be testing the ability of FES PET and FDG PET to measure the pharmacologic effect of endocrine-targeted therapy and early measures that may help predict response to such targeted agents. In patients on selective estrogen receptor degrader (SERD) therapies, where repeat FES PET is used primarily to evaluate residual ER availability rather than tumor response, repeat FDG PET may be omitted, as determined by requirements of the co-enrolling companion therapeutic protocol. A subset of patients may undergo a third FES PET at a later time point determined by the treatment regimen.

FDG PET and CT will be used as staging tests for this study and FDG will also serve as a comparator for tumor localization with the FES imaging. Patients will have a clinical FDG PET scan prior to the start of treatment as part of their standard care; their treating physician will order this. In rare cases where an FDG PET has recently been performed at an outside medical facility but the scan has (1) inadequate image quality or (2) insufficient quantitative information, or for patients who would not be ordered as a standard part of the patient's care, a baseline FDG scan will be done as part of this protocol. A second FDG PET scan will be done as a study procedure concurrent with the FES PET timing stipulated by treatment regimen (this may vary from 1 to 12 weeks post treatment start depending on regimen). In the subset of patients undergoing a third

FES PET scan there may also be a research FDG PET done at the same time point if determined by the treatment regimen.

[figure not shown]

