### **6.3.3 Rationale**

- 6.3.3.a** The primary hypothesis to be tested is that pre-therapy and post-therapy [F]FES uptake will measure the effect of endocrine-targeted therapy on ER expression and/or estradiol binding to the ER.
- 6.3.3.b** This single-site study will determine the ability of [F]FES to quantify changes in ER expression and estradiol binding in vivo in patients with breast cancer for whom endocrine-targeted therapy has been chosen based on clinical presentation or as part of therapeutic clinical trial. The results of this trial will help evaluate the effect of ER-directed therapies on ER expression and estrogen binding to ER, and secondarily whether the FES PET measures of estrogen receptor function, and changes with treatment, predict response to endocrine targeted therapy in patients with known ER+ primary or metastatic breast cancer as measured by immunohistochemistry (IHC) of biopsy material. The primary goal is to gain insight into the efficacy of ER-targeted therapies, especially novel therapies, on ER expression and estrogen binding to ER. For example, serial FES PET imaging could be used to test the efficacy of an ER antagonist in blocking estradiol binding, or the ability of an agent directed at altering ER expression to change ER expression levels in tumors. Such in vivo measures of the pharmacodynamics of ER-directed therapy have traditionally required serial biopsy and have been quite challenging. FES PET presents a non-invasive alternative to measure the effects of ER-directed therapy.
- 6.3.3.c** We have examined the role of FES in 47 heavily pretreated patients (Linden, 2006). Initial FES uptake was measured and correlated with subsequent tumor response to 6 months of hormonal treatment. In this

study, 11/47 (23%) patients had an objective response. Quantitative FES uptake and response were significantly associated; 0/15 patients with initial FES SUV < 1.5 responded to hormonal therapy, compared to 11/32 (34%) with FES SUV ≥ 1.5 ( $p < .01$ ). In the subset of patients whose tumors did not over-express HER2/neu, 11/24 (46%) of patients with SUV ≥ 1.5 responded. These pilot results support the further evaluation of the predictive capability of FES PET.

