- 6.3.3.d** FES uptake predicted a greater likelihood of response to endocrine therapy. Patients with low or absent FES uptake were unlikely to manifest a response to treatment, yet FES did not help to distinguish which patients would experience a clinical benefit, defined as stable disease. Several factors may have contributed to this finding. Stable disease over 6 months included patients with disease that may have progressed slowly, independent of treatment, as well as patients with rapidly progressive disease in whom therapy slowed but did not abrogate tumor growth. The study was not designed to distinguish between these two outcomes. In addition, we identified PgR (progesterone receptor) expression as contributing to likelihood of response, and noted that elevated estradiol levels and HER2 expression were associated with non-response. In this new study we propose to document tumor characteristics including quantitative ER mRNA levels measured by PCR and semi-quantitative levels of ER, PgR, AR and HER2 by IHC. Gathering these indices as part of the proposed study may help to enhance the predictive value of PET FES, allow understanding of mechanism of resistance to endocrine therapy, and potentially determine which patients are likely to appreciate clinical benefit as a result of endocrine therapy, even in the absence of an objective response.
- 6.3.3.e** In prior observational imaging trials (unpublished data) we have measured regional estrogen-ER binding using FES PET before and after treatment with estrogen depleting therapies, Aromatase inhibitors (AI), and estrogen blocking therapies, Tamoxifen (TAM), or fulvestrant (FUL) in 30 metastatic breast cancer patients. As expected, tumor FES uptake declined markedly on ER blockers TAM and FUL (average 54% decline), but less than 15% on average on estrogen-depleting AIs ( $p < 0.001$ ). All 5/5 patients taking TAM showed complete tumor blockade (FES SUV ≤ 1.5 after treatment), compared to 4/11 of FUL patients ( $p = 0.009$ ). We concluded that molecular imaging can assess the *in vivo* pharmacodynamics of targeted agents, and may give insight into the activity of established therapeutic agents.

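### Does the optional proportion reaching a target follow-up FES SUV need a fixed target and a baseline condition in the plan?

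*Combined protocol and SAP*

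**What the plan says.** Section 6.14.1 (Analysis Plan) is a general plan for pilots of about 20 patients. Its expected primary analysis is a one-sample test of percent change in FES SUV. It then lists, as possible further analyses, two proportions in one sentence: patients who reach some threshold of percent change, or patients who "surpassed a targeted follow-up FES SUV value". Either would be given with a 90% Wilson interval. Table 6.3 shows such intervals at n = 20, 25 and 30.

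The assessments are in Section 6.10.2. Part (a) lists FES SUV at each scan and, separately, "percentage and SUV unit change in SUV between baseline and repeat FES PET scan". Part (c) records average and maximum SUV per site and adds: "For each subject, we will calculate the average and range of FES uptake values for active disease sites". It also covers lesions with little or no FES signal, since regions are transferred from FDG images, "especially in ER-negative tumors which are not visualized on FES imaging".

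The Schema (6.1) says that in SERD patients "repeat FES PET is used primarily to evaluate residual ER availability rather than tumor response".

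The only post-treatment cut is in the background, Section 6.3.3.e: "All 5/5 patients taking TAM showed complete tumor blockade (FES SUV ≤ 1.5 after treatment"), "compared to 4/11 of FUL patients". Section 6.3.3.c gives a baseline figure from an earlier series: "0/15 patients with initial FES SUV < 1.5 responded to hormonal therapy". Section 6.14.1 refers to neither.

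**The concern.** Four things needed to compute the second proportion are not stated: the target, whether passing it means going above or below, which SUV summary represents the patient, and what to do with patients already past the target at baseline.

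The last matters most. Eligibility (6.4.1) requires ER positivity by immunohistochemistry and a site of at least 1.5 cm, but no minimum FES uptake. A patient whose uptake is below a downward target before treatment, and stays there, is a success although the drug did nothing. The study's primary objective is to measure the effect of therapy, and Section 6.3.3.e describes a follow-up SUV at or below 1.5 as blockade without stating a baseline condition. A reader could therefore take the proportion as the share of patients in whom the drug worked. It would then mix drug effect with the share who started low.

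**Working it through.** **Plan's own figures.** The Wilson interval is [p + z²/2n ± z√(p(1−p)/n + z²/4n²)] / (1 + z²/n), with z = 1.645. For 6/20 this gives 0.164 to 0.484, against 0.16 to 0.48 printed. All 15 intervals in Table 6.3 reproduce to two decimals.

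**Size under the drug-effect reading.** Assume a downward target of 1.5, borrowed from 6.3.3.e. Let f be the share already at target at baseline and p the true crossing rate among the rest. If baseline-low patients stay low, the all-patient proportion is f + (1 − f)p. The value of f for these pilots is unknown. The range below is an assumption, with 15/47 = 0.319 (90% Wilson 0.22 to 0.44) from 6.3.3.c as its upper end.

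| f | Successes in 20 if p = 0 | Shown if p = 0.25 | Shown if p = 0.50 |
|---|---|---|---|
| 0 | 0 | 0.25 | 0.50 |
| 0.10 | 2.0 | 0.325 | 0.55 |
| 0.20 | 4.0 | 0.40 | 0.60 |
| 0.319 | 6.4 | 0.489 | 0.66 |

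The distortion could be large at the upper end and vanishes at f = 0.

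**How firm these inputs are.** The 15/47 comes from a heavily pretreated series, whereas 6.4.1 also admits primary disease. It uses a cut of below 1.5 rather than at or below 1.5. The assumption that low patients stay low is also too strong. With mean change 0 and SD 25 points (6.14.1), a baseline of 1.4 rises above 1.5 with probability 1 − Φ((1.5/1.4 − 1)·100/25) = 1 − Φ(0.286) = 0.39. That SD describes change in treated patients, so it may exceed pure measurement noise.

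**What restricting to patients not already at target would do.** At f = 0.319 about 20 × 0.681 = 13.6, say 14, patients remain. At an observed 50% the 90% interval goes from 0.33–0.67 (10/20) to 0.30–0.70 (7/14). Noise near the cut remains: with no drug effect and the same SD, a baseline of 1.8 falls to 1.5 or lower with probability Φ((1.5/1.8 − 1)·100/25) = Φ(−0.667) = 0.25, and a baseline of 2.0 with probability Φ(−1) = 0.16. The restricted proportion therefore has its own upward bias.

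**Which reading the text supports.** The sentence in 6.14.1 sets a change-based proportion beside a follow-up-level proportion, and the section names measures of uptake and measures of change as separate endpoints. A patient who starts low and does not move has zero percent change and is not a success on the change-based proportion. The plan thus already provides a proportion for drug effect. The level-based one answers how much ER remains available on therapy, which is the purpose the Schema and Section 6.6.2.e give for the repeat scan in SERD patients. For that question every patient belongs in the denominator.

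**The case for a change.** The best case for a change is that the text is silent on all four items, and an analyst could pick target, direction and SUV summary after seeing the data. The drug-effect reading is also not far-fetched, given the primary objective and the way 6.3.3.e speaks of blockade. A few sentences and a cross-table of baseline against follow-up status would settle it without extra scans.

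The silence is real, and so is the freedom to choose late. But the analysis is optional and descriptive, and no test or decision rests on it. Regimens and scan times differ between pilots, so a single target in the general plan is not to be expected, although the documents do not say where a pilot would record its own. The background paragraph is a short summary of unpublished data. It reports average declines from baseline (54% on blockers, under 15% on aromatase inhibitors) before the 1.5 cut, and does not show whether those patients began above 1.5. It cannot establish how 6.14.1 will be read.

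The proposed remedies have costs of their own. Restricting the denominator changes the question, loses precision and leaves bias near the cut. Adding Table 6.3 columns at 14 to 18 patients would write an assumed baseline share into the protocol, whereas the table only illustrates precision by n.

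**Conclusion.** No change follows. Section 6.14.1 leaves detail open in an optional analysis, and as worded that analysis is a valid description of FES level on therapy. The figures above (2 to 6 spurious successes in 20; a true 50% shown as 55% to 66%) arise only if three things hold together: a pilot reads the proportion as drug effect, it uses a downward target near 1.5, and 10% to 32% of its patients start at or below that target. None of these is in the analysis plan. The percent-change test and the percent-change proportion do not depend on the target and are unaffected.

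An analyst who uses this proportion would, as ordinary practice, state the target, direction and SUV summary beforehand, call the result a follow-up level rather than a change, and show baseline status beside it. The baseline SUVs needed for this are already collected under 6.10.2.a.
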